9.4.1.2.1 SUPPORTIVE CARE GUIDELINES FOR PEMBROLIZUMAB

Subjects should receive appropriate supportive care measures as deemed necessary by the treating investigator. Suggested supportive care measures for the management of AEs with potential immunologic etiology are outlined along with the dose modification guidelines in [Section 9.4.1.2](#). Where appropriate, these guidelines include the use of oral or IV treatment with corticosteroids, as well as additional antiinflammatory agents if symptoms do not improve with administration of corticosteroids. Note that several courses of steroid tapering may be necessary as symptoms may worsen when the steroid dose is decreased. For each disorder, attempts should be made to rule out other causes such as metastatic disease or bacterial or viral infection, which might require additional supportive care. The treatment guidelines are intended to be applied when the investigator determines the events to be related to pembrolizumab.

Note: If after the evaluation of the event, it is determined not to be related to pembrolizumab, the investigator does not need to follow the treatment guidance. Refer to [Section 9.4.1.2](#) for guidelines regarding dose modification and supportive care.

It may be necessary to perform additional procedures such as bronchoscopy, endoscopy, or skin photography as part of evaluation of the event.

Table 5 below shows treatment guidelines for subjects who experience an infusion reaction associated with administration of pembrolizumab.

Table 5 Infusion Reaction Treatment Guidelines		
NCI CTCAE Grade	Treatment	Premedication at subsequent dosing
Grade 1 Mild reaction; infusion interruption not indicated; intervention not indicated	Increase monitoring of vital signs as medically indicated until the subject is deemed medically stable in the opinion of the investigator.	None
Grade 2 Requires infusion interruption but responds promptly to symptomatic treatment (eg, antihistamines, NSAIDs, narcotics, IV fluids); prophylactic medications indicated for ≤ 24 h	Stop Infusion and monitor symptoms. Additional appropriate medical therapy may include but is not limited to: IV fluids Antihistamines NSAIDs Acetaminophen Narcotics Increase monitoring of vital signs as medically indicated until the subject is	Subject may be premedicated 1.5h (± 30 minutes) prior to infusion of pembrolizumab with: Diphenhydramine 50 mg orally (or equivalent dose of antihistamine).

Table 5 Infusion Reaction Treatment Guidelines		
NCI CTCAE Grade	Treatment	Premedication at subsequent dosing
	
deemed medically stable in the opinion of the investigator.
 
If symptoms resolve within one hour of stopping drug infusion, the infusion may be restarted at 50% of the original infusion rate (eg, from 100 mL/h to 50 mL/h). Otherwise dosing will be held until symptoms resolve and the subject should be premedicated for the next scheduled dose.
 
Subjects who develop Grade 2 toxicity despite adequate premedication should be permanently discontinued from further study treatment administration.
	Acetaminophen 500-1000 mg orally (or equivalent dose of antipyretic).

Grades 3 or 4
 
Grade 3: Prolonged (ie, not rapidly responsive to symptomatic medication and/or brief interruption of infusion); recurrence of symptoms following initial improvement; hospitalization indicated for other clinical sequelae (eg, renal impairment, pulmonary infiltrates)
 
Grade 4: Life-threatening; pressor or ventilatory support indicated
	
Stop Infusion.
 
Additional appropriate medical therapy may include but is not limited to:
 
 Epinephrine** IV fluids Antihistamines NSAIDs Acetaminophen Narcotics Oxygen Pressors Corticosteroids 
Increase monitoring of vital signs as medically indicated until the subject is deemed medically stable in the opinion of the investigator.
 
Hospitalization may be indicated.
 
**In cases of anaphylaxis, epinephrine should be used immediately.
 
Subject is permanently discontinued from further study drug treatment.
	No subsequent dosing

Appropriate resuscitation equipment should be available in the room and a physician readily available during the period of drug administration.
		

Table 5 Infusion Reaction Treatment Guidelines		
NCI CTCAE Grade	Treatment	Premedication at subsequent dosing

ANC = absolute neutrophil count, CTCAE = Common Terminology Criteria for Adverse Events v4.03, h = hour, IV = intravenous, NCI = National Cancer Institute, NSAID = nonsteroidal antiinflammatory drug.

9.4.2 Identity of Investigational Products

Lenvatinib and pembrolizumab will be supplied by the sponsor in appropriately labeled containers.

[figure not shown]
Lenvatinib will be provided as 4-mg and 10-mg capsules. Lenvatinib is formulated with calcium carbonate, mannitol, microcrystalline cellulose, hydroxypropylcellulose, low-substituted hydroxypropylcellulose, and talc.

Pembrolizumab may be provided as a sterile, preservative-free, white to off-white lyophilized powder in single-use vials. Each vial will be reconstituted and diluted for IV infusion. Each 2 mL of reconstituted solution contains 50 mg of pembrolizumab and is formulated in L-histidine (3.1 mg), polysorbate-80 (0.4 mg), sucrose (140 mg). The solution may contain hydrochloric acid/sodium hydroxide to adjust pH to 5.5.

Alternatively, pembrolizumab may be provided as a sterile, preservative-free, clear to slightly opalescent, colorless to slightly yellow solution that requires dilution for IV infusion. Each vial contains 100 mg of pembrolizumab in 4 mL of solution. Each 1 mL of solution contains 25 mg of pembrolizumab and is formulated in: L-histidine (1.55 mg), polysorbate 80 (0.2 mg), sucrose (70 mg), and Water for Injection.

9.4.2.1 Chemical Name, Structural Formula of Lenvatinib

LENVIMA is the mesylate salt of lenvatinib. Its chemical name is 4-[3-chloro-4-(N'-cyclopropylureido)phenoxy]-7-methoxyquinoline-6 carboxamide methanesulfonate. The molecular formula is C₂₁H₁₉ClN₄O₄ • CH₄O₃S, and the molecular weight of the mesylate salt is 522.96. The chemical structure of lenvatinib mesylate is:

9.4.2.2 Information of Pembrolizumab

Pembrolizumab is a potent humanized immunoglobulin G4 (IgG4) mAb with high specificity of binding to the programmed cell death 1 (PD-1) receptor, thus inhibiting its interaction with

programmed cell death ligand 1 (PD-L1) and programmed cell death ligand 2 (PD-L2). Based on preclinical in vitro data, pembrolizumab has high affinity and potent receptor blocking activity for PD-1. Pembrolizumab has an acceptable preclinical safety profile and is in clinical development as an IV immunotherapy for advanced malignancies. Keytruda™ (pembrolizumab) is indicated for the treatment of patients across a number of indications. For more details on specific indications refer to the Investigator's Brochure.

9.4.2.3 Labeling for Study Drug

Lenvatinib and pembrolizumab will be labeled in accordance with text that is in full regulatory compliance with each participating country and is translated into the required language(s) for each of those countries.

9.4.2.4 Storage Conditions

Study drugs will be stored in accordance with the labeled storage conditions. Temperature monitoring is required at the storage location to ensure that the study drug is maintained within an established temperature range. The investigator or is responsible for ensuring that the temperature is monitored throughout the total duration of the study and that records are maintained; the temperature should be monitored continuously by using either an in-house validated data acquisition system, a mechanical recording device, such as a calibrated chart recorder, or by manual means, such that minimum and maximum thermometric values over a specific time period can be recorded and retrieved as required.

9.4.3 Method of Assigning Subjects to Treatment Groups

This is an open-label, single-arm study. All subjects who provide signed informed consent to participate in this study and satisfy all eligibility requirements (see [Section 9.3](#)) will receive lenvatinib in combination with pembrolizumab. There is no randomization in this study.

9.4.4 Selection of Doses in the Study

For the assessment of MTD, the lenvatinib doses selected are 24 mg, 20 mg, and 14 mg QD all in combination with 200 mg pembrolizumab Q3W given IV. While 24 mg is the recommend dose for locally recurrent or metastatic, progressive, radioactive iodine-refractory differentiated thyroid cancer ([LENVIMA Package Insert/SmPC](#)), 20 mg and 14 mg are the first and second doses in lenvatinib's dose reduction scheme for all tumors (except hepatocellular carcinoma) for which data are available. While 2 mg/kg is the recommended dose for pembrolizumab for melanoma ([KEYTRUDA Package Insert/SmPC](#)), a 200 mg Q3W fixed dose regimen is planned to be used in this study (see [Section 7.2](#)).

9.4.5 Selection and Timing of Dose for Each Subject

Lenvatinib will be administered with water orally once a day (with or without food) in 21-day cycles at approximately the same time each day. Treatment cycles will be counted continuously regardless of dose interruptions. On D1 of each cycle, it will be administered approximately within 1 hour after completion of pembrolizumab administration.

Pembrolizumab will be administered as a dose of 200 mg as a 30-minute IV infusion, Q3W (infusion durations of 25 minutes to 40 minutes are acceptable). The Pharmacy Manual contains specific instructions for the preparation of the pembrolizumab infusion and its administration. Subjects should maintain a normal diet unless modifications are required to manage an AE such as diarrhea, nausea or vomiting. Study treatment of pembrolizumab may be administered up to 3 days before or after the scheduled D1 of each cycle due to administrative reasons.

9.4.6 Blinding

The study will not be blinded.

9.4.7 Prior and Concomitant Therapy

Prior therapy must be documented by the following criteria prior to entry into study.

- Any single agent therapy, and any combination of cytotoxic, hormonal, biological targeted agents, and/or humanized antibodies, scheduled to be administered as a preplanned treatment, given concomitantly, sequentially or both, is considered 1 regimen.
- Planned neoadjuvant chemotherapy (to debulk the tumor prior to surgical intervention) plus postoperative adjuvant chemotherapy is considered 1 regimen.
- For chemotherapy: if, due to toxicity, the dosing of one or more of the components must be reduced, or one or more of the components of the regimen must be omitted, or one of the components must be replaced with another similar drug, the changed version of the original regimen is not considered a new regimen. However, if a new component, dissimilar to any of the original components, is added to the regimen, the new combination is considered a new regimen.
- For prior VEGF/VEGFR-targeted agents, treatment with each agent will be counted individually, regardless of the duration of administration.
- If the treatment is interrupted for surgery or radiotherapy or any other reason and then continues with an unchanged schedule and components, that treatment is considered as 1 regimen despite the interruption.

All prior medications (including over-the-counter medications) administered 30 days before the first dose of study drug and any concomitant therapy administered to the subject during the course of the study (starting at the date of informed consent) until 30 days after the final dose of study drug will be recorded. Additionally, all diagnostic, therapeutic, or surgical procedures relating to malignancy should be recorded. Any medication that is considered necessary for the subject's health and that is not expected to interfere with the evaluation of or interact with lenvatinib or pembrolizumab may be continued during the study.

Treatment of complications or AEs, or therapy to ameliorate symptoms (including blood products, blood transfusions, fluid transfusions, antibiotics, and antidiarrheal drugs), may be given at the discretion of the investigator, unless it is expected to interfere with the evaluation of (or to interact with) lenvatinib or pembrolizumab.

Aspirin, nonsteroidal antiinflammatory drugs, and low-molecular-weight heparin (LMWH) are permissible but should be used with caution. Granulocyte colony-stimulating factor or equivalent may be used in accordance with American Society of Clinical Oncology (ASCO), institutional, or national guidelines. Erythropoietin may be used according to ASCO, institutional, or national guidelines, but the subject should be carefully monitored for increases in red blood cell counts.

The investigator will record on the Adverse Event CRF any AE for which the concomitant medication/therapy was administered.

9.4.7.1 Drug–Drug Interactions

Lenvatinib's weak in vitro inhibitory and induction potential on cytochrome P450 (CYP) enzymes (Study No. XT063020) suggests a low risk of lenvatinib interference with the PK of other drugs metabolized by CYP P450 enzymes which are co-administered in usual clinic practice. Nonclinical studies identify CYP3A4 as an important enzyme responsible for human hepatic metabolism of lenvatinib. However, clinical studies conducted to test these findings showed that co-administration of lenvatinib with CYP3A4/P-glycoprotein (P-gp) inhibitors or inducers is not of clinical concern (see [Appendix 5](#) for a summary of clinical findings).

No formal pharmacokinetic drug interaction studies have been conducted with pembrolizumab. Pembrolizumab is a mAb; pharmacokinetic interactions with lenvatinib (and vice-versa) are not expected.

9.4.7.2 Prohibited Concomitant Medications/Vaccinations

Medications or vaccinations specifically prohibited in the exclusion criteria are not allowed during the ongoing study. If there is a clinical indication for any medication or vaccination specifically prohibited during the study, discontinuation from study therapy or vaccination may be required. The investigator should discuss any questions regarding this with the Sponsor Clinical Director. The final decision on any supportive therapy or vaccination rests with the investigator and/or the subject's primary physician. However, the decision to continue the subject on study therapy or vaccination schedule requires the mutual agreement of the investigator, the sponsor, and the subject.

9.4.7.2.1 PROHIBITED CONCOMITANT MEDICATIONS

Subjects should not receive other antitumor therapies while on study. If a subject receives additional antitumor therapies, such as chemotherapy, hormone therapy, palliative radiotherapy, or immunotherapy, this will be judged to represent evidence of disease progression, and continuation of the study medication and further participation in the study must be discussed and agreed upon with the sponsor.

Subjects are prohibited from receiving the following therapies during the Screening and Treatment Phase of this study:

- Anticancer therapies such as chemotherapy, TKIs, antitumor interventions (surgical resection, thoracentesis, etc.), or immunotherapy
- Investigational agents other than lenvatinib and pembrolizumab
- Radiation therapy

Note: Radiation therapy to a symptomatic solitary lesion or to the brain may be considered as an exception on a case by case basis after consultation with the Sponsor. Administration of palliative radiation therapy will be considered clinical progression for the purposes of determining PFS.

- Live vaccines within 30 days prior to the first dose of study treatment and while participating in the study. Examples of live vaccines include, but are not limited to, the following: measles, mumps, rubella, chicken pox, yellow fever, rabies, Bacille Calmette-Guérin (BCG), and typhoid (oral) vaccine. Seasonal influenza vaccines for injection are generally killed virus vaccines and are allowed. However, intranasal influenza vaccines (eg, Flu-Mist[®]) are live attenuated vaccines, and are not allowed.
- Systemic glucocorticoids for any purpose other than to modulate symptoms from an event of suspected immunologic etiology. The use of physiologic doses of corticosteroids may be approved after consultation with the sponsor.

Note: Inhaled steroids are allowed for management of asthma or seasonal allergies.

For subjects who, in the assessment by the investigator, require the use of any of the aforementioned treatments for clinical management, continuation of the study medication and further participation in the study must be discussed and agreed upon with the sponsor. Subjects may receive other medications that the investigator deems to be medically necessary.

The Exclusion Criteria describes other medications that are prohibited in this clinical study.

For clarification, the following concomitant medications are also **allowed**:

- Thyroid hormone suppressive therapy (including therapy to treat hypothyroidism and hyperthyroidism)
- Adjuvant hormonal therapy for history of definitively treated breast or prostate cancer
- Anticoagulants including LMWH, warfarin, anti-Xa agents
- Antiinflammatory agents (n.b., use of steroids is not permitted except as outlined in [Sections 9.4.1.2.1](#) to manage immune-related AEs)
- Bisphosphonates or denosumab
- Supportive care guideline for pembrolizumab (see [Section 9.4.1.2.1](#))
- Antihypertensive therapy (including additional antihypertensive treatment as appropriate if BP increases once the patient has been enrolled)

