9.7.1.1.2 SECONDARY ENDPOINTS (BOTH PHASE 1B AND PHASE 2)

The secondary efficacy endpoints will be ORR, PFS, OS, DCR, CBR, DOR, and durable SD rate (SD ≥ 23 weeks) by irRECIST as appropriate. The secondary efficacy endpoints are defined as follows.

- **ORR** is defined as the proportion of subjects who have BOR of irCR or irPR at the time of data cutoff.
- **PFS** is defined as the time from the first study dose date to the date of first documentation of confirmed disease progression or death (whichever occurs first). If a subject has not experienced disease progression or death, then the subject's data will be censored at the date of the last available tumor assessment.
- **OS** is measured from the start date of the treatment period until date of death from any cause. Subjects who are lost to follow-up and the subjects who are alive at the date of data cutoff will be censored at the date the subject was last known alive.
- **DCR** is defined as the proportion of subjects who have BOR of irCR or irPR or irSD (duration of irSD ≥ 5 weeks).
- **CBR** is defined as the proportion of subjects who have BOR of irCR or irPR or durable irSD (duration of irSD ≥ 23 weeks).
- **DOR** is defined as the time from the date the criteria are met for an irCR or irPR (whichever is recorded first) to the date the disease progression is objectively

documented. If a subject has no record of disease progression, then the subject's data will be censored at the last available tumor assessment.

- **Durable SD rate** is defined as the proportion of subjects whose BOR is irSD and the duration of irSD is ≥ 23 weeks.

Determination of the plasma PK profile of lenvatinib while subjects are receiving combination therapy also is a secondary endpoint.

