5.2.5 Prior and Concomitant Therapy

All investigator terms for medications recorded on the CRF will be coded using the World Health Organization (WHO, Geneva, Switzerland) Drug Dictionary using the March 2016 version or later. The number (percent) of subjects who have taken prior and concomitant medications will be summarized on the Full Analysis Set, by Anatomical Therapeutic Chemical (ATC) Classification and WHO drug preferred term. Prior medications will be defined as medications that stopped prior to the first dose of study drug. Concomitant medications will be defined as medications that (1) have started before the first dose of study drug and are continuing at the time of the first dose of study drug, or (2) have started on or after the date of the first dose of study drug up to 30 days following the last dose of study drug. A medication that cannot be determined as prior/concomitant/post-treatment due to missing/incomplete dates will be regarded as a concomitant medication. The summary of concomitant, including anti-hypertensive, anti-diarrheal and corticosteroid medications/therapies will be provided.

Prior anti-cancer therapies including anti-cancer medications, anti-cancer procedures and radiotherapy will be summarized and listed. Data listings will be provided for all prior and concomitant medications.

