data will be censored at the date of the last adequate radiologic assessment. The PFS censoring rules in this SAP and definition of progression date follow the principles of the Food and Drug Administration (FDA) “[Guidance for Industry Clinical Trial Endpoints for the Approval of Cancer Drugs and Biologics \(2007\)](#)”. Due to the use of pembrolizumab, all tumor assessments up to the first PD identified under irRCIST are considered as long as the subjects did not start a new anti-cancer therapy. The date of radiological assessment is based on the date of scans performed for a time point. The date will be based on the time point required CT/MRI scans unless there is a new lesion on the bone scan(s) or brain scan(s) performed to ensure CR or PR, or on brain scan(s) performed to ensure CR. Table 5 shows the censoring rules for the derivation of PFS.

Table 5 Censoring rules for the derivation of PFS.

No.	Situation	Date of Event (Progression/Death) or Censoring	Outcome
1	No baseline tumor assessments	Date of first dose	Censored
2	Progression documented between scheduled visits	Date of first radiologic PD assessment	Event
3	No progression	Date of last adequate radiologic assessment	Censored
4	New anticancer treatment started	Date of last adequate radiologic assessment prior to or on date of new anticancer treatment	Censored
5	Death before first PD assessment	Date of death	Event
6	Death between adequate assessment visits*	Date of death	Event
7	Death or progression after more than one missed visit/tumor assessment**	Date of last adequate radiologic assessment before missed tumor assessments	Censored

CR = complete response, PD = progressive disease, PR = partial response, SD =stable disease,

* Adequate tumor assessment is radiologic assessment at regular interval as defined in the protocol.

** More than one missed visit/adequate tumor assessment is defined as having the duration between the last adequate tumor assessment and death or PD being longer than 14 weeks - 1 day, which is 97 days ($= ((6+1) \times 2 \times 7) - 1$) for subjects on the every 6 week tumor assessment schedule in the first 8 cycles of treatment and 20 weeks - 1 day, which is 139 days ($= ((9+1) \times 2 \times 7) - 1$) for subjects on the every 9 week tumor assessment schedule after Cycle 8 in this study.

The priority of the censoring rules is as follows,

1. If the subject had PD or death, the following sequence will be applied:

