- If a subject did not have a baseline tumor assessment (No. 1), the subject will be censored on the

date of first dose.

- If the subject died within 97 days (14 weeks -1 day) following first dose and did not receive a new anticancer treatment, it will be counted as PFS event at the date of death.
- If a subject had new anticancer treatment before PD or death (No. 4), the subject will be censored on the date of the last adequate tumor assessment prior to or on the date of new anticancer treatment.
- If a subject missed two or more tumor assessments before PD or death (No. 7), the subject will be censored on the date of the last adequate tumor assessment before PD or death. Note that if a subject is censored by both this criterion and the anticancer treatment criterion, the earliest censoring date will be used.
- Otherwise, if a subject had an event (No. 2, No. 5, or No. 6), the earliest event date will be used.

2. If a subject did not have PD or death, the censoring date will be the earliest censoring date if the subject met multiple censoring criteria (No. 1, No. 3, No. 4, No. 7).

The distribution of PFS and time curve will be estimated using Kaplan–Meier method. Median time to PFS and 95% CI will be provided for each cohort. Three-month, 6-month, 9-month, and 12-month PFS rate will be estimated using the Kaplan–Meier method and corresponding 95% CIs will be provided.

Overall Survival (OS): OS is measured from the start date of the treatment phase until date of death from any cause. All events of death will be included, regardless of whether the event occurred while the subject was still taking study drug, or after the subject discontinued study drug. If a subject has no record of death, then the data will be censored at the date the subject was last known to be alive, or the data cutoff date, whichever is earlier (see Table 6 for censoring rules). The distribution of OS and time curve will be estimated using Kaplan–Meier method. Median survival time and the corresponding 95% CI, survival rates at 12, 18, and 24 months, and corresponding 95% CIs will be estimated using Kaplan–Meier method for each treatment cohort.

Table 6 Censoring Rules for Overall Survival Endpoint

Situation	Event Date or Censoring	Outcome
Death during study	Date of death	Death
Death after data cut-off	Date of data cut-off	Censored
Subject still alive at data cut-off	Date of data cut-off	Censored

Situation	Event Date or Censoring	Outcome

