7 CHANGES IN THE PLANNED ANALYSES

Not applicable.

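### SAP Table 6 censors living subjects at the data cutoff, against the OS text in both documents, and no row of SAP Table 5 carries out the protocol's rule that palliative radiotherapy is progression for PFS

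*Protocol*

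**What the plan says.** **OS.** Protocol 9.7.1.1.2 and SAP 5.1.2 censor a subject who is alive at cutoff on the date last known alive. Protocol 9.7.1.6.2 and the OS paragraph of SAP 5.4.3 use the earlier of that date and the cutoff date, and the SAP paragraph refers the reader to Table 6. Table 6 row 3 then censors the living subject on the cutoff date. Only row 4, for subjects lost to follow-up, uses the date last known alive.

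**PFS.** Protocol 9.4.7.2.1 treats receipt of "additional antitumor therapies, such as chemotherapy, hormone therapy, palliative radiotherapy, or immunotherapy" as evidence of progression. It allows some on-study radiotherapy: "Radiation therapy to a symptomatic solitary lesion or to the brain may be considered as an exception on a case by case basis". It then adds: "Administration of palliative radiation therapy will be considered clinical progression for the purposes of determining PFS". Protocol 9.7.1.1.2 and SAP 5.4.3 define the PFS event as confirmed progression or death, with no mention of radiotherapy or clinical progression. In SAP Table 5, row 4 censors a subject who starts new anticancer treatment, at the "Date of last adequate radiologic assessment prior to or on date of new anticancer treatment". The priority list closes the set of events: "if a subject had an event (No. 2, No. 5, or No. 6), the earliest event date will be used". Those three rows are radiologic progression or death.

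**Related text.** Item (3) of the best-overall-response rules in SAP 5.4 uses tumor assessments only while no new anti-cancer therapy has started. SAP Section 7 declares no change from the planned analyses.

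**The concern.** A programmer who follows Table 6 literally gets different OS times from one who follows the sentence introducing it. The table's version can only lengthen follow-up. It keeps a subject in the risk set after the last contact, when a death would not be known. With no control arm, the error has nothing to cancel against.

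For PFS, a protocol rule makes an occurrence an event, and the SAP row that most naturally receives it makes it a censoring. The two treatments point in opposite directions, and row 4 gives a PFS curve at or above the one under Protocol 9.4.7.2.1. The same classification feeds the best-response rule. If on-study palliative radiotherapy is new anti-cancer therapy there, a confirming scan taken after it is dropped. A response could then be lost from ORR(Week 24), the Phase 2 primary endpoint, and from DOR.

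**Working it through.** **The plan's own arithmetic.** The Table 5 windows for missed assessments reproduce: (6+1)×2×7−1 = 97 days and (9+1)×2×7−1 = 139 days. No stated figure depends on the two conflicts.

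**OS: where the rules differ**

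| Subject | OS definitions | Analysis text | Table 6 |
|---|---|---|---|
| Contact on or after cutoff confirms alive at cutoff | last known alive | cutoff | cutoff |
| Last contact before cutoff, status not verified, not classed as lost | last contact | last contact | cutoff (row 3) |
| Lost to follow-up | last known alive | last known alive | last known alive (row 4) |
| Withdrew consent | not named | last known alive | no row |

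Only the second line gives a real difference in censoring time between the analysis text and the table. Off-treatment contact was every 12 weeks (Protocol 9.1.3.2, before Amendment 09), and neither document describes a status check at cutoff, so such subjects are to be expected.

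**OS: size.** Kaplan–Meier: S(t) = Π(1 − d/n). Row 3 keeps unverified subjects in n after last contact, while their deaths cannot enter d.

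- From the documents: N = 120, contact every 3 weeks on treatment and every 12 weeks after; landmarks 12, 18 and 24 months. Protocol 9.1 sets a cohort's cutoff once subjects complete 8 cycles or stop early, so the shortest lag after last entry is 8×3 = 24 weeks.
- Assumed: exponential survival with median 12 or 18 months, uniform accrual over 12, 18 or 24 months, median 7 months on treatment, deaths learned at the next contact.

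Table 6 minus text rule, in percentage points, status unverified, cutoff 24 weeks after last entry:

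| Accrual | 12 months | 18 months | 24 months |
|---|---|---|---|
| 12 months | 2.0–2.4 | beyond follow-up | beyond follow-up |
| 18 months | 1.2–1.4 | 2.7–2.9 | beyond follow-up |
| 24 months | 0.8–1.0 | 1.6–1.8 | 2.8 |

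For example, with 12-month accrual and a 12-month median, the 12-month rate is 0.500 under the text and 0.524 under Table 6 (true 0.500).

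The lag drives the result. At 12 months after last entry the gap is 0.1–0.2 points at the 12-month landmark and 0.8–2.0 at 18 months. At an 18-month lag it is at most 0.2 at both, and 0.6–1.5 at 24 months. At a 24-month lag it is at most about 0.2 throughout. With status verified at cutoff, Table 6 is within 0.2 points of the truth at any lag. If deaths are updated to cutoff but survivors are not, the text rule is itself 0.8–2.8 points too low.

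**PFS: the rules in order**

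1. Protocol 9.4.7.2.1: palliative radiotherapy is progression for PFS. No event date is given.
2. Protocol 9.7.1.1.2 and SAP 5.4.3: the event is confirmed progression or death.
3. Table 5: no row names radiotherapy. Row 4 is the natural fit, because the protocol lists palliative radiotherapy among antitumor therapies and SAP 5.2.5 counts radiotherapy among prior anti-cancer therapies. Row 4 censors.
4. The same tension holds for the other therapies in the protocol sentence (chemotherapy, hormone therapy, immunotherapy): evidence of progression in the protocol, censored by row 4.

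**PFS: size.** The documents give no radiotherapy rate and no PFS median. Assumed: exponential times with median 5 to 10 months, a share f of PFS endings being palliative radiotherapy, other progression dated at the next scheduled scan. Six-month PFS, event versus row-4 censoring:

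| Median | f = 2% | f = 5% |
|---|---|---|
| 5 months | 0.465 vs 0.472 | 0.464 vs 0.483 |
| 7 months | 0.579 vs 0.586 | 0.577 vs 0.594 |
| 10 months | 0.682 vs 0.687 | 0.681 vs 0.694 |

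One such subject before month 6 moves the 6-month rate by a mean of 3.2–4.1 points at N = 20 and 0.5–0.7 at N = 120.

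**Scale.** The approximate 95% half-width at a 50% rate is 1.96×√(0.25/120) = 8.9 points at N = 120 and 1.96×√(0.25/20) = 21.9 at N = 20.

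**The case against.** The best defence of Table 6 is that row 3 was meant for subjects known to be alive at cutoff. For them it agrees with the analysis text and is correct. Lost subjects have their own row, and the sentence citing the table already covers consent withdrawals. That stands and limits the point, but row 3 does not say the status must be verified, and the definitions in both documents still read differently.

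The best defence of Table 5 is that the SAP follows the protocol's own endpoint section, and that Protocol 9.5.1.3 rests all efficacy endpoints other than OS on tumor assessments. That also stands: the conflict lies largely inside the protocol, between a note on concomitant therapy and its endpoint definition. It still needs settling, because the note speaks expressly of determining PFS.

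Derivation rules sit in separate documents (SAP Section 9) and may already resolve both matters. The effects are small beside the sampling error.

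Four stronger readings are not supported. A reader might infer that Table 5 leaves radiotherapy with no rule at all; row 4 is a plausible home. A reader might infer that Table 6 always inflates OS; it does so only where status is unverified. A reader might take the end of survival follow-up under Amendment 09 as making the bias large; the SAP is based on Amendment 8, and the documents do not place an OS cutoff after that change. Finally, a reader might assume ORR(Week 24) is untouched, or that it is harmed. The documents establish neither.

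**Conclusion.** Both conflicts are in the text, and the SAP should be corrected.

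For OS, Table 6 row 3 contradicts the definitions in both documents. It contradicts the analysis text whenever last contact precedes cutoff and status at cutoff is unverified. The upward bias is about 1 to 3 points at landmarks within follow-up for a 24-week cutoff lag, falling to about 0.2 points or less at 24 months and to near zero where status is verified. The documents do not fix the lag for the OS analysis; they also refer to a cutoff for the final analysis, which may be later.

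For PFS, no Table 5 row carries out Protocol 9.4.7.2.1, and row 4 would reverse it. The effect is 0.5–0.7 points at 6 months if radiotherapy makes up 2% of PFS endings and 1.4–1.8 points at 5%. No shift in median PFS is claimed.

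Every size rests on assumed medians, accrual and radiotherapy use. PFS and OS are secondary and descriptive. Whether ORR(Week 24) and DOR are reached depends on a classification that the SAP has not made for on-study radiotherapy.

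**What to change.** **OS.** Reword Table 6 row 3 to the date last known alive, or the data cutoff if earlier. State that deaths and survivors are ascertained to the same date. A separate row for withdrawal of consent is optional clarification. A vital-status check at cutoff is possible only where survival follow-up is still running.

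**PFS.** Reconcile Protocol 9.4.7.2.1, Protocol 9.7.1.1.2, the PFS definition in SAP 5.4.3 and Table 5. State in Table 5 and its priority list whether on-study palliative radiotherapy, and other added antitumor therapy, is an event or is censored, and on what date. Which rule is primary is the sponsor's choice. Report the other as a sensitivity analysis, and declare any departure from Protocol 9.4.7.2.1 in SAP Section 7.

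**Best response.** State whether on-study palliative radiotherapy counts as new anti-cancer therapy under item (3) of the best-response rules in SAP 5.4.

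**Cost.** A few lines of text, mostly in the SAP, and one PFS sensitivity run. No design change and no new data collection, apart from site contact if the optional status check is done. The best-response statement fixes a rule that the primary analysis uses, so it should be settled before the data are analyzed.
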